# 2.2 Endpoints

# 2.2.1 Primary Endpoint

• Objective response rate will include confirmed complete response (CR) + confirmed partial response (PR) and will be determined as per RECIST 1.1 or MD Anderson Criteria (for bone-only metastatic disease)

# 2.2.2 Secondary Endpoints

- Adverse events are defined by the NCI Common Terminology Criteria for Adverse Events (NCI CTCAE) v4
- Progression-free survival is defined as the time from Day 1 of treatment until the criteria for disease progression is met as defined by RECIST 1.1 or death as a result of any cause.
- Overall survival is defined as the time from Day 1 of treatment until death as a result of any cause

Version Date: 15MAY2019 Confidential Page 24 of 60

## 3. ELIGIBILITY CRITERIA

#### 3.1 Inclusion Criteria

Subject must meet all of the following applicable inclusion criteria to participate in this study:

- 1. Written informed consent and HIPAA authorization for release of personal health information prior to registration. **NOTE:** HIPAA authorization may be included in the informed consent or obtained separately.
- 2. Age  $\geq$  18 years at the time of consent.
- 3. ECOG Performance Status of  $\leq 1$  within 14 days prior to registration. Cisplatin-ineligible chemotherapy-naïve subjects (see inclusion criteria #9) may have an ECOG Performance Status of  $\leq 2$ .
- 4. Histological or cytological evidence/confirmation of urothelial cancer.
- 5. Metastatic and/or unresectable (cT4b) urothelial cancer.
- 6. Metastatic disease evaluable on imaging studies. Subjects may have measurable disease according to RECIST 1.1 or bone-only disease within 30 days prior to registration.

**NOTE**: Bone-only subjects are eligible if their disease can be documented/evaluated by bone scans, CT or MRI. Their disease will be assessed using MD Anderson criteria.

**NOTE**: Previously irradiated lesions are eligible as a target lesion only if there is documented progression of the lesion after irradiation.

7. Somatic alteration considered pathogenic/likely pathogenic in one of the following DDR genes as determined by genomic sequencing performed in a Clinical Laboratory Improvement Amendments (CLIA) laboratory. Somatic alterations will include nonsense, frameshift, splice-site or missense mutations or homozygous deletions. Subjects with alterations in DDR genes not included in the list below will be considered on a case by case basis after discussion with the sponsor-investigator(s). Subjects with germline alterations in DDR genes will be considered on a case by case basis and will be reviewed by the sponsor-investigator(s). At least 6 subjects will have BRCA or ATM alterations.

Nucleotide Excision Repair	Homologous Recombination		DNA Sensor	Fanconi Ai Pathway	nemia	Base Excision Repair	Other
ERCC2	BRCA1	RAD52	ATM	PALB2	FANCE	XRCC2	MUTYH
ERCC3	BRCA2	RAD54L	ATR	BRIP1	FANCF	XRCC3	RECQL4
ERCC4	RAD50	NBN	MDC1	FANCA	FANCG	XRCC4	POLQ
ERCC5	RAD51	MRE11A	ATRX	FANCB	BLM	XRCC5	POLE
ERCC6	RAD51B	RAD51D	CHEK1	FANCC		XRCC6	WRN
	RAD51C	CTIP	CHEK2	FANCD2			

Version Date: 15MAY2019 Confidential Page 25 of 60

- 8. A subject with prior brain metastasis may be considered if they have completed their treatment for brain metastasis at least 4 weeks prior to study registration, have been off corticosteroids for  $\geq 2$  weeks, and are asymptomatic
- 9. Subjects must have progressed despite at least 1 prior line of treatment for metastatic and/or unresectable urothelial cancer. However, cisplatin-ineligible (defined by a calculated creatinine clearance of >30 but < 60 mL/min **OR** CTCAE v4 Grade ≥ 2 audiometric hearing loss **OR** CTCAE v4 Grade ≥ 2 peripheral neuropathy **OR** ECOG PS = 2) and chemotherapynaïve subjects are also eligible.
- 10. Prior cancer treatment (systemic therapy or radiation therapy) must be completed at least 3 weeks prior to registration and the subject must have recovered from all reversible acute toxic effects of the regimen (other than alopecia) to Grade ≤ 1 or baseline.
- 11. Demonstrate adequate organ function as defined in the table below. All screening labs to be obtained within 28 days prior to registration.

System	Laboratory Value
Hematological	
Absolute Neutrophil Count (ANC)	$\geq 1.5 \times 10^9 / L$
Hemoglobin (Hgb)	$\geq$ 9 g/dL
Platelets	$\geq 100 \text{ x } 10^9/\text{L}$
Renal	
Calculated creatinine clearance 	> 30 mL/min
Hepatic	
Bilirubin	$\leq 1.5 \times \text{upper limit of normal (ULN)}$
Aspartate aminotransferase (AST)	$\leq 2.5 \times \text{ULN (or } \leq 5 \times \text{ULN if liver metastases)}$
Alanine aminotransferase (ALT)	$\leq 2.5 \times \text{ULN (or } \leq 5 \times \text{ULN if liver metastases)}$

- 1 Cockcroft-Gault formula will be used to calculate creatinine clearance (See SPM)
- 12. Female subjects must be postmenopausal or there must be evidence of non-childbearing status for women of childbearing potential: negative urine or serum pregnancy test within 28 days of study treatment and confirmed prior to treatment on Day 1. Postmenopausal is defined as:
  - Amenorrheic for 1 year or more following cessation of exogenous hormonal treatments
  - Luteinizing hormone (LH) and Follicle stimulating hormone (FSH) levels in the postmenopausal range for women under 50
  - radiation-induced oophorectomy with last menses >1 year ago
  - chemotherapy-induced menopause with >1 year interval since last menses
  - surgical sterilization (bilateral oophorectomy or hysterectomy)
- 13. Females of childbearing potential must be willing to abstain from heterosexual activity or to use 2 forms of highly effective methods of contraception from the time of informed consent until 90 days after treatment discontinuation. The two contraception methods can be comprised of two barrier methods, or a barrier method plus a hormonal method. Males must be willing to abstain from heterosexual activity or to use 2 forms of highly effective methods

Version Date: 15MAY2019 Confidential Page 26 of 60

of contraception from the time of informed consent until 90 days after treatment discontinuation.

Acceptable non-hormonal birth control methods:

- Total sexual abstinence ie, refrain from any form of sexual intercourse in line with the patients' usual and/or preferred lifestyle. Periodic abstinence (eg, calendar ovulation, symptothermal, post-ovulation methods) and withdrawal are not acceptable methods of contraception.
- Vasectomised sexual partner PLUS male condom. With participant assurance that partner received post-vasectomy confirmation of azoospermia.
- Tubal occlusion PLUS male condom
- Intrauterine Device PLUS male condom. Provided coils are copper-banded.

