	5. Metastatic and/or unresectable (cT4b) urothelial cancer.				
	6. Metastatic disease evaluable on imaging studies. Subjects may have measurable disease according to RECIST 1.1 or bone-only disease within 30 days prior to registration.  NOTE: Bone-only subjects are eligible if their disease can be documented/ evaluated by bone scans, CT or MRI. Their disease will be assessed using MD Anderson criteria. NOTE: Previously irradiated lesions are eligible as a target lesion only if there is documented progression of the lesion after irradiation.				
	7. Somatic alteration considered pathogenic/likely pathogenic in one of the following DDR genes as determined by genomic sequencing performed in a Clinical Laboratory Improvement Amendments (CLIA) laboratory. Somatic alterations will include nonsense, frameshift, splice-site or missense mutations or homozygous deletions. Subjects with alterations in DDR genes not included in the list below will be considered on a case by case basis after discussion with the sponsor-investigator. Subjects with germline alterations in DDR genes will be considered on a case by case basis and will be reviewed by the sponsor-investigator. At least 6				

subjects will have BRCA or ATM alterations.					
Nucleotide	Homologous		Base	Other	
Excision	Recombina	ation	Excision		
Repair			Repair		
ERCC2	BRCA1	RAD52	XRCC2	MUTYH	
ERCC3	BRCA2	RAD54L	XRCC3	RECQL4	
ERCC4	RAD50	NBN	XRCC4	POLQ	
ERCC5	RAD51	MRE11A	XRCC5	POLE	
ERCC6	RAD51B	RAD51D	XRCC6	WRN	
	RAD51C	CTIP			
DNA Sensor	Fanconi A	nemia			
	Pathway				
ATM	PALB2	FANCE			
ATR	BRIP1	FANCF			
MDC1	FANCA	FANCG			
ATRX	FANCB	BLM			
CHEK1	FANCC				
CHEK2	FANCD2				

- 8. A subject with prior brain metastasis may be considered if they have completed their treatment for brain metastasis at least 4 weeks prior to study registration, have been off of corticosteroids for ≥ 2 weeks, and are asymptomatic.
- 9. Subjects must have progressed despite at least 1 prior line of treatment for metastatic and/or unresectable urothelial cancer. However, cisplatin-ineligible (defined by a calculated creatinine clearance of > 30 but < 60 mL/min OR CTCAE v4 Grade ≥ 2 audiometric hearing loss OR CTCAE v4 Grade ≥ 2 peripheral neuropathy OR ECOG PS = 2), chemotherapy-naïve subjects are also eligible.

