# 1.2 Current Standard of Care

While metastatic urothelial cancer is a relatively chemotherapy sensitive neoplasm with response rates to first-line platinum-based chemotherapy of approximately 40-60%, responses are generally short-lived and the median progression free survival is only 8-9 months. In 2016, the PD-L1 inhibitor atezolizumab became the first treatment approved by the United States Food and Drug Administration for patients with platinum-resistant metastatic urothelial cancer. However, durable responses to single-agent PD-1/PD-L1 blockade are only achieved in a small minority of patients with metastatic urothelial cancer (approximately 15-20% of patients) highlighting the critical need for the development of additional novel therapeutic strategies.

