# 9.8.5 Objective Response Rate

The objective response rate is the proportion of all subjects with confirmed PR or CR according to RECIST 1.1, from the start of treatment until disease progression/recurrence (taking as reference for progressive disease the smallest measurements recorded since the start of treatment).

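### Entry does not require progression since the most recent systemic therapy, so a response to that therapy that is still deepening at baseline can be counted as an olaparib response

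*Combined protocol and SAP*

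**What the plan says.** Section 3.1, criterion 9 (repeated as synopsis item 9) sets the progression requirement: "Subjects must have progressed despite at least 1 prior line of treatment for metastatic and/or unresectable urothelial cancer". Any one prior line satisfies it.

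An exemption follows. The synopsis words it for cisplatin-ineligible subjects who have had no chemotherapy: "chemotherapy-naïve subjects are also eligible". Section 3.1 inserts a conjunction, "and chemotherapynaïve subjects are also eligible", which can be read as two separate exempt groups. Under either wording, exempt subjects need no prior progression, and being chemotherapy-naïve does not rule out earlier treatment with a drug that is not chemotherapy.

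Criterion 10 sets the washout: "Prior cancer treatment (systemic therapy or radiation therapy) must be completed at least 3 weeks prior to registration". Criterion 6 sets the disease window: "Subjects may have measurable disease according to RECIST 1.1 or bone-only disease within 30 days prior to registration".

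Criterion 6 also contains the one lesion-level safeguard. A previously irradiated lesion may be a target only if "there is documented progression of the lesion after irradiation". Exclusion 5 bars investigational drugs within 30 days of registration. Neither covers a standard systemic drug.

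Under Sections 9.5 and 9.8.2, a partial response is a fall of at least 30% from the baseline sum of diameters, confirmed no less than four weeks later. Section 12.4.1 counts everyone who takes at least one dose. Section 12.3 sizes the study at 27 against a 10% null.

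**The concern.** There is no control arm. The response rate can be read as an olaparib effect only if tumours would not have been shrinking without olaparib. Progression since the last treatment is the usual support for that assumption, and criterion 9 does not ask for it.

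Two routes into the trial leave the gap open:

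- A subject progresses on platinum, then takes a PD-1/PD-L1 inhibitor and stops it for toxicity while responding. The platinum progression satisfies criterion 9.
- A cisplatin-ineligible, chemotherapy-naïve subject has just stopped a PD-1/PD-L1 inhibitor. No progression is needed.

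Both are foreseeable. Section 1.2 describes this drug class as approved treatment and puts its durable responses at approximately 15–20% of patients. If shrinkage from such a drug continues past the olaparib baseline, the primary endpoint credits it to olaparib.

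**Working it through.** **Step 1. Reproduce the design (Section 12.3).** Let X be the number of responders, binomial with n = 27.

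- P(X ≥ 5 | 0.10) = 0.1266, above 0.05.
- P(X ≥ 6 | 0.10) = 0.0471, the stated actual alpha.
- P(X ≥ 6 | 0.28) = 0.8093, the stated 81% power.

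The implied boundary is therefore 6 of 27. The plan does not write it as a decision rule; it follows from the stated alpha.

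**Step 2. Check whether another criterion closes the gap.**

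| Prior treatment | Protection in the plan |
|---|---|
| Radiation to a target lesion | Lesion must have progressed since irradiation (criterion 6) |
| Investigational drug | None within 30 days of registration (exclusion 5) |
| Standard systemic drug | 3-week washout only (criterion 10); no progression since that drug required |

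**Step 3. Compare the baseline window with the washout.** Disease may be documented up to 30 days before registration, and the last prior dose may be 21 days before it. So the scan can precede that dose by up to 30 − 21 = 9 days. If the 28-day screening window in the study calendar also binds and runs to registration, the overlap is 28 − 21 = 7 days. If it runs to Cycle 1 Day 1, the overlap is shorter and may vanish.

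**Step 4. Identify what would be scored.** Response is measured from the study baseline, so shrinkage before it does not count. Stable disease or a maintained response scores as stable disease. A false response needs a further fall of at least 30% after baseline, or disappearance of the remaining disease, with confirmation.

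**Step 5. Size.** Suppose m of the 27 subjects enter with a residual response to their last drug. Each has total probability p of being scored a confirmed response, and the other 27 − m respond at the null rate of 10%. The documents give neither m nor p; both are assumptions.

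P(6 or more) = Σ over j = 0..m of C(m, j) p^j (1 − p)^(m − j) × P(Bin(27 − m, 0.10) ≥ 6 − j)

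Example with m = 1, p = 0.30: 0.70 × P(Bin(26, 0.10) ≥ 6) + 0.30 × P(Bin(26, 0.10) ≥ 5) = 0.70 × 0.0399 + 0.30 × 0.1118 = 0.0615.

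| Assumed p | m = 1 | m = 2 | m = 3 |
|---|---|---|---|
| 0.10 | 4.7% | 4.7% | 4.7% |
| 0.15 | 5.1% | 5.4% | 5.8% |
| 0.20 | 5.4% | 6.2% | 7.1% |
| 0.30 | 6.2% | 7.9% | 9.9% |
| 0.50 | 7.6% | 11.6% | 17.0% |

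At p = 0.10 there is no inflation, because these subjects then respond at the null rate. Below 0.10 the figure falls under 4.7%. Each carry-over response adds 1/27 = 3.7 percentage points to the observed rate.

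**The case against.** **The response criteria already filter most carry-over.** A reader might infer that any ongoing response to the last drug would be scored for olaparib. The documents do not support that: the 30% fall is measured from the new baseline and must be confirmed. This objection stands, and it limits the point to responses still deepening after baseline.

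**The cited background does not supply the probability.** Section 1.2 reports that "durable responses to single-agent PD-1/PD-L1 blockade are only achieved in a small minority of patients with metastatic urothelial cancer". Durability concerns responses that last. It says nothing about a further 30% shrinkage after the drug is stopped. This also stands. Values of p from 0.30 to 0.50 have no basis in the documents, so the table starts at the null rate.

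**The washout is not the only safeguard.** Besides the two protections in the Step 2 table, criterion 10 requires recovery from reversible toxicity to Grade 1 or baseline, and exclusion 12 lists a history of pneumonitis among its examples. These narrow the group that stopped a checkpoint inhibitor for toxicity. They do not close the gap for standard systemic drugs.

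**The exempt group is limited.** A reader might infer that every chemotherapy-naïve subject is a risk. A subject with no prior systemic therapy has no last drug to carry over. Criterion 3 and the synopsis also treat the exempt group as cisplatin-ineligible and chemotherapy-naïve together.

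**The objective is estimation.** The planned report is a response rate with an exact 95% interval, and no success rule is written. That is fair. At 6 of 27 (22.2%) the interval runs from 8.6% to 42.3%, so one carry-over response, worth 3.7 points, is small against sampling error. Unlike sampling error, though, it pushes the estimate in one direction and the interval does not reflect it.

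**The response-rate definition is not at fault.** The Section 9.8.5 phrase "from the start of treatment until disease progression/recurrence" sets the observation period. It says nothing about prior therapy and neither causes nor cures the problem.

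**Conclusion.** The gap in eligibility is real. Progression on some prior line is enough, the exempt group needs none, and nothing requires progression since the last standard systemic drug. The baseline window can also reach back past that drug's last dose. A response to it that is still deepening can therefore enter the primary endpoint.

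The size cannot be determined from the documents. With one to three such subjects, the chance of reaching 6 responders under the null runs from 4.7% (no inflation) at an assumed p of 0.10 to 17.0% with three subjects at p = 0.50. A reader might take larger figures from fixed counts: 11.2%, 23.6% or 43.6% if one, two or three carry-over responses are certain. Those are conditional on the responses having happened; nothing in the documents shows they are likely.

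This is a cheap improvement to the attribution of the primary endpoint. It is not an error in the sample-size calculation, which reproduces.

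**What to change.** - **Criterion 9 and synopsis item 9.** Require that subjects with prior systemic therapy for metastatic or unresectable disease have documented progression on or after the most recent such therapy. Exempt only subjects with no such therapy.
- **Baseline scan.** State that it must follow the last dose of prior therapy.
- **Wording.** Reconcile the exemption in Section 3.1 with the synopsis, so that it is clear whether one group or two is meant.
- **Subjects already enrolled.** Add a supportive response rate with exact 95% confidence interval, excluding those without progression since their last therapy. Prior cancer treatment history is collected at screening (study calendar, footnote 1). Each subject's progression status after the last line should be confirmed from it.

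Cost: a few candidates who stopped their last therapy without progression would wait or not be enrolled, and some may need a repeat scan. The supportive estimate is slightly less precise than the primary one. The sample size of 27, the implied boundary of 6, alpha of 0.0471 and power of 80.9% are unchanged.

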# 5.2.1.4 Contraception

# Olaparib is regarded as a compound with medium/high fetal risk.

Women of childbearing potential and their partners, who are sexually active, must agree to the use of TWO highly effective forms of contraception in combination [as listed below], throughout the period of taking study treatment and for at least 90 days after last dose of study drug(s), or they must totally/truly abstain from any form of sexual intercourse (see below).

Male subjects and their partners, who are sexually active and of childbearing potential, must agree to the use of TWO highly effective forms of contraception in combination [as listed below], throughout the period of taking study treatment and for 90 days after last dose of study drug(s) due to the unknown effects of the study drug on the sperm, or they must totally/truly abstain from any form of sexual intercourse (see below). Male subjects should not donate sperm throughout the period of taking study treatment and for 90 days following the last dose of study drug(s).

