# Acceptable non-hormonal birth control methods:

- Total sexual abstinence ie, refrain from any form of sexual intercourse in line with the patients' usual and/or preferred lifestyle. Periodic abstinence (eg, calendar ovulation, symptothermal, post-ovulation methods) and withdrawal are not acceptable methods of contraception.
- Vasectomised sexual partner PLUS male condom. With participant assurance that partner received post-vasectomy confirmation of azoospermia.
- Tubal occlusion PLUS male condom
- Intrauterine Device PLUS male condom. Provided coils are copper-banded.

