## Acceptable hormonal methods:

- Etonogestrel implants (eg, Implanon®, Norplant®) PLUS male condom
- Normal and low dose combined oral pills PLUS male condom
- Hormonal shot or injection (eg, Depo-Provera) PLUS male condom
- Intrauterine system device (eg, levonorgestrel-releasing intrauterine system Mirena®) PLUS male condom

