# 7. STUDY CALENDAR & EVALUATIONS

Study Evaluation Cycle = 28 days	Screening	Treatment	Tumor	Safety Follow Up Visit 	Survival Follow Up 
	-28 days	Cycle 1 + Day 1 ± 2 days	Assessments  ± 7 days	30 Days Post Treatment (±7 days)	Every 3 Months (±7 days)
REQUIRED ASSESSMENTS					
Informed Consent	X				
Medical History 	X				
Physical Exam	X	X		X	
Vital signs and ECOG Performance Status 	X	X		X	
Documentation of DDR alteration in CLIA lab assay 	X				
ECG 	$X^4$				
AEs & Concomitant Medications	X	X		X	
LABORATORY ASSESSMENTS					
Complete Blood Cell Count with diff (CBC) 	X	X		X	
Comprehensive Metabolic Profile (CMP) 	X	X		X	
PT/INR and aPTT 	X				
Pregnancy test (serum or urine) (WOCBP) 	X	$X^7$			
Urinalysis	X				
DISEASE ASSESSMENT					
CT of chest 	X		$X^8$		
CT or MRI of abdomen and pelvis 	X		$X^8$		
Bone Scan 	X		X8		
TREATMENT EXPOSURE					
Olaparib		X			
CORRELATIVE SAMPLES					
Archival Tumor Tissue 	X				
Collection of tumor tissue obtained as standard of care 				$X^{10}$	
Blood Samples for correlative research 		$X^{11}$		$X^{11}$	
BANKING SAMPLES					
Whole Blood 		$X^{12}$		$X^{12}$	
FOLLOW-UP					
Survival Status, Subsequent Therapy					X

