# **Key to Footnotes**

- 1: Medical History should include the following information: (1) Diagnosis and staging to include Tumor Node Metastasis (TNM) staging (2) smoking history, (3) trial awareness question (4) prior cancer treatment history and (5) genetic sequencing information.
- 2: Vital signs to include blood pressure, weight, and height (screening only) and ECOG performance status.
- 3: The laboratory report indicating the presence of a DDR alteration (see eligibility) from a CLIA laboratory is required for registration.
- 4: ECG is required within 7 days prior to starting study treatment.
- 5: If screening (baseline) CBC and CMP were performed within 7 days of Day 1 of treatment, these do not need to be repeated. CMP to include sodium, potassium, chloride, creatinine, blood urea nitrogen; liver function tests (LFTs) to include AST, ALT, total bilirubin, alkaline phosphatase
- 6: Subjects taking warfarin may participate in this study; however, it is recommended that prothrombin time (INR and APTT) be monitored carefully at least once per week for the first month, then monthly if the INR is stable.
- 7: For women of childbearing potential (WOCBP): urine or serum βhCG will be checked at screening and prior to study drug on Cycle 1 Day 1 (only if clinically appropriate). If a urine test is done and it is positive or cannot be confirmed as negative, a serum pregnancy test will be required.
- 8: Tumor imaging to continue near the end of every 2nd cycle (~every 8 weeks) for the first 12 months following Cycle 1 Day 1. After 12 months, tumor assessments will be performed near the end of every 3rd cycle (~every 12 weeks). Imaging selected for each subject should remain the same throughout the study. Bone scan will be obtained at screening if there is any clinical or laboratory suspicion of metastatic bone involvement. If bone scan is positive at baseline for metastases, it will be included with tumor response assessments as noted above.

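### The study calendar makes the Cycle 1 Day 1 pregnancy test optional although criterion 12 requires it, and criterion 13 permits two barrier methods although no listed pair consists of two barriers.

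*Combined protocol and SAP*

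**What the plan says.** **Pregnancy testing.** Section 3.1 opens with "Subject must meet all of the following applicable inclusion criteria to participate in this study". Criterion 12 then asks, for women of childbearing potential, for a "negative urine or serum pregnancy test within 28 days of study treatment and confirmed prior to treatment on Day 1". The synopsis carries the same requirement. Neither place qualifies it.

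The section 7 calendar has a row headed "Pregnancy test (serum or urine) (WOCBP", marked at screening and, with footnote 7, in the treatment column. That footnote begins by limiting itself to women of childbearing potential. It calls for a check at screening and "prior to study drug on Cycle 1 Day 1 (only if clinically appropriate".

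**Contraception.** Criterion 13 in section 3.1, and again in the synopsis, states: "The two contraception methods can be comprised of two barrier methods, or a barrier method plus a hormonal method". In section 3.1 a list of acceptable methods follows under the same criterion. Section 5.2.1.4 repeats the list and makes it binding: women of childbearing potential and their partners, if sexually active, "must agree to the use of TWO highly effective forms of contraception in combination [as listed below". Typical entries are "Tubal occlusion PLUS male condom" and "Normal and low dose combined oral pills PLUS male condom".

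**The concern.** In each case one part of the protocol allows what another part does not.

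- **Day 1 test.** A site that follows footnote 7 may decide the Day 1 test is not needed and treat on the screening result alone. Criterion 12 would then be unmet.
- **Contraception.** A site that follows the sentence in criterion 13 may accept a woman using two barrier methods, a combination that section 5.2.1.4 does not offer. A reader of the synopsis sees that sentence without the list.

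What is at stake is fetal exposure to a drug whose fetal risk section 5.2.1.4 rates as medium to high. Pregnancy is an exclusion (section 3.2, criterion 2), and section 11.1.5.2 requires olaparib to stop at once if it occurs. Either lapse is also an eligibility or treatment deviation that the protocol's own wording would have invited. The response rate, the sample size and the analysis are not touched.

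**Working it through.** The plan gives no figure to reproduce. The check compares the texts and makes two counts.

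**1. Day 1 pregnancy test**

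| Source | Who | Screening test | Check before first dose |
|---|---|---|---|
| Criterion 12 (section 3.1 and synopsis) | Women of childbearing potential | Required, within 28 days of treatment | Required, unconditional |
| Section 7, footnote 7 | Women of childbearing potential | Required | Conditional on clinical appropriateness |

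Two readings that would remove the conflict were considered.

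- *The condition only filters out women who cannot become pregnant.* This fails. Both the calendar row and the opening of footnote 7 already restrict the test to women who can.
- *The condition excuses a repeat when the screening test is recent.* The protocol writes such waivers out: footnote 5 excuses repeat blood counts and chemistry if done within 7 days of Day 1. Footnote 7 gives no interval, no criterion and no decision-maker, so in practice the decision falls to the site.

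Scheduled tests: screening (1) + Cycle 1 Day 1 (1) = 2 under criterion 12. If the condition is judged not met, 2 − 1 = 1. Footnote 7 names no later test, so a skipped one is not made up. The oldest negative result at first dose is then the screening limit of 28 days, against a confirmation before dosing on Day 1.

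**2. Contraceptive pairs**

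Non-abstinence pairs listed in section 3.1 and repeated in section 5.2.1.4:

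| Method combined with a male condom | Type | Two barriers? | Barrier plus hormonal? |
|---|---|---|---|
| Vasectomised partner | Non-hormonal | No | No |
| Tubal occlusion | Non-hormonal | No | No |
| Copper intrauterine device | Non-hormonal | No | No |
| Implant | Hormonal | No | Yes |
| Combined oral pill | Hormonal | No | Yes |
| Injection | Hormonal | No | Yes |
| Levonorgestrel intrauterine system | Hormonal | No | Yes |

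Total: 3 + 4 = 7. Each pair contains exactly one barrier, the male condom.

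- Two-barrier pairs: 0 of 7.
- Barrier plus hormonal: 4 of 7.
- Pairs that fit neither combination named in criterion 13: 7 − 4 − 0 = 3 of 7.

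The sentence is therefore wrong in both directions. It admits a combination that is not listed, and it leaves out three that are.

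**The case against.** **On the test.** Criterion 12 speaks of confirmation and does not expressly say a second assay. It could be read as verifying negative status before dosing, with a repeat assay left to judgement. Even on the stricter reading, the lead-in to section 3.1 still binds, so a footnote cannot waive an eligibility criterion; the likely harm is confusion rather than authorised dosing. The second argument is fair as to formal precedence. The first is strained, because footnote 7 itself places a hormone assay at Cycle 1 Day 1, so the protocol plainly has a test in mind there. If the word is unclear, that is a further reason to align the two texts.

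**On contraception.** In section 3.1 the list follows directly, so a site would have to stop reading mid-criterion to go wrong. The documents do not define a barrier method, and the two named combinations may be shorthand for the list's two headings. The synopsis also refers readers to section 3 for the full criteria. All this lowers the practical risk, but the sentence and the list still disagree.

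**On scale and remedy.** Few women are likely to be affected, possibly none, and no statistical result moves. That stands. It is also true that a woman using two barriers is already outside section 5.2.1.4, so the correction narrows nothing that section allows. Finally, section 5.2.2.2 warns that olaparib may reduce the efficacy of hormonal contraceptives, and four of the seven listed pairs rely on one. Pointing to the list does not settle that caution, although each of those pairs also includes a condom.

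**Conclusion.** Both inconsistencies hold. Footnote 7 makes conditional a check that criterion 12 requires. At worst, the first dose rests on a single negative test that is 28 days old, where the criterion calls for confirmation before dosing on Day 1. Criterion 13 allows a type of pair that appears 0 times among the 7 listed.

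The point is minor and concerns patient safety and consistent conduct, not inference. It should be corrected because the correction is cheap and the protocol itself treats fetal exposure as a material risk.

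The conclusion rests on two assumptions: that confirmation in criterion 12 means a test, and that vasectomy, tubal occlusion and intrauterine devices are not barrier methods, which is the ordinary classification. The number of women of childbearing potential is not given. It is probably small, and enrolment is at most 30.

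**What to change.** Apply the stricter rule that the protocol already contains.

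1. In section 7, footnote 7, delete the parenthetical condition, so that the Cycle 1 Day 1 test is required for every woman of childbearing potential.
2. In criterion 13, in both section 3.1 and the synopsis, replace the sentence on permitted combinations with: *The two methods must be one of the combinations listed in Sections 3.1 and 5.2.1.4.* Replace the whole sentence. Striking out only the two-barrier option would leave barrier plus hormonal as the sole combination named, which covers 4 of the 7 listed pairs and omits the 3 non-hormonal ones.

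The cost is one deletion and one replaced sentence in two places, made by amendment, with a check that the consent form agrees. For subjects it means one urine or serum test already on the calendar. Any woman enrolled on two barrier methods would need to change to a listed pair, which section 5.2.1.4 already requires.
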